## 6.2 Exploratory Analyses

For exploratory analyses, mean total FSFI change from baseline will be compared across the study groups using a simple independent Student's  $t$ -test

$$t = \frac{(\bar{X}_1 - \bar{X}_2) - \delta_0}{s}$$

where equal variances are assumed

$$s = \sqrt{\frac{s_1^2}{n_1} + \frac{s_2^2}{n_2}}$$

and

J3 Bioscience, Inc.	Statistical Analysis Plan	CI03-SAP Rev. 00 Page 14 of 31
	CI03: A Clinical Investigation to Evaluate Efficacy of the J3 Bioscience Lubricating Intravaginal Ring VR101 as a Personal Lubricant Device in Women	

$$DF = \frac{(VAR_1 + VAR_2)^2}{\frac{VAR_1^2}{n_1 - 1} + \frac{VAR_2^2}{n_2 - 1}}$$

a confidence interval for the difference between group means will be calculated,

$$(\bar{X}_1 - \bar{X}_2) - t_{\alpha/2}(S) \text{ to } (\bar{X}_1 - \bar{X}_2) + t_{\alpha/2}(S)$$

where  $t_{\alpha/2}$  is the inverse cumulative probability of a t distribution at  $1 - \alpha/2$ , and effect size, Cohen's  $d$  is the standardized mean difference using the pooled standard deviation.

Independent Student's  $t$ -tests will also be calculated using group means for each of the FSFI domains. No adjustment for multiplicity is planned for the exploratory analyses. The broader population results of the exploratory analyses will be presented in tabular form.

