5.3 Study Participants

5.3.1 Inclusion Criteria for Participant Selection (ICH E3; 9.3 ICH E9; 2.2.1)

Clinical Investigation Participants Must:

1. Completely understand and sign the informed consent form (ability to read and understand the consent form in the English language).
2. Be at least 21 years of age.
3. Express willingness to comply with the entire study visit schedule (see Table 7 in study procedures section).
4. Over the course of the study:
 - a. Abstain from the use of any vaginal moisturizers or lubricants or any other topically applied vaginal products not provided by study staff during the entirety of study participation
 - b. Abstain from using lubricated or spermicide-containing male or female condoms
 - c. Abstain from vaginal intercourse with a male partner using a lubricated condom

J3 Bioscience, Inc.	Clinical Investigation Plan and Protocol CI03	CI03-CIP Rev. 02 Page 26 of 60
	A Clinical Investigation to Evaluate Efficacy of the J3 Bioscience Lubricating Intravaginal Ring VR101 as a Personal Lubricant Device in Women	

- d. Abstain from any oral sex during or prior to vaginal intercourse with a male partner.
- e. Must not initiate, modify or discontinue a regimen of HRT (hormone replacement therapy) or estrogen-containing birth control.

NOTE: women who have been using non-vaginal HRT or estrogen-containing birth control (e.g., oral, transdermal) on a regular dosing interval continuously for at least 3 months may continue on the same regimen during the study

- f. Abstain from use of any other vaginally-placed devices (e.g. ring, diaphragm, cervical cap, pessary products)
 - g. If able to get pregnant, use an approved method of contraception (per remainder of I/E criteria) to reduce their risk of becoming pregnant during the study.
- 5. In the previous 3 months, have had or attempted sexual intercourse with a male partner a minimum of twice per month (on average).
 - 6. Respond to all 4 individual FSFI Lubrication Questions (7 - 10) with a score of 1, 2, or 3.
 - 7. Attempt sexual intercourse at least 4 times during the 4-week double-blind study.

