5.4.6 FSFI (Female Sexual Function Index) Survey

During both study visits (and an Early Termination Visit, if applicable), each participant will be given the FSFI Survey (see Appendix A).

J3 Bioscience, Inc.	Clinical Investigation Plan and Protocol CI03	CI03-CIP Rev. 02 Page 35 of 60
	A Clinical Investigation to Evaluate Efficacy of the J3 Bioscience Lubricating Intravaginal Ring VR101 as a Personal Lubricant Device in Women	

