8.1.2 Exploratory

An exploratory analysis of individual changes in the Female Sexual Function Index (FSFI) total composite score (Rosen 2000) and its domains (Desire, Arousal, Lubrication, Orgasm, Satisfaction, and Pain) during 28 days of use will be conducted. Similar to the analyses conducted by Rosen 2000, changes in individual scores will be compared for the two groups using appropriate parametric (independent-test) or nonparametric (Mann-Whitney) statistical methods.

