8.7.3 Unavoidable Loss of Data

- It is understood that data may still be missing, for anticipated and unanticipated reasons (intercurrent events) that arise during the study. As no universally applicable methods for handling missing values are recommended in the guidance documents, methods for handling missing values in this study will be justified by reasons for missingness and predefined by updating this aspect in the statistical analysis plan during the blind review. An investigation will be made concerning the sensitivity of the results of analysis to the method of handling missing values.

It is expected that any study subject who begins one of the treatment arms following randomization will be included in the primary efficacy analysis. As noted, randomization criteria require all inclusion criteria are met and that screening (Day 0) FSFI-LD scores are complete. The primary efficacy outcome, proportion of subjects who have a “functional” score of 4.5 or more after 4 weeks of treatment, is therefore dependent on a post randomization FSFI-LD score.

- Where unavoidable, participants who cannot complete 28 days of treatment will be scheduled for an End of Treatment visit so that final FSFI-LD scores can be collected prior to withdrawal of consent.

J3 Bioscience, Inc.	Clinical Investigation Plan and Protocol CI03	CI03-CIP Rev. 02 Page 44 of 60
	A Clinical Investigation to Evaluate Efficacy of the J3 Bioscience Lubricating Intravaginal Ring VR101 as a Personal Lubricant Device in Women	

- For subjects who must drop out prior to providing study endpoint efficacy data the reason for early discontinuation will be ascertained and recorded in the CRF. Prior to data lock and unblinding of the randomization code the status and quality of each subject's study data will be assessed by the sponsor's data quality team. The disposition and assignment of each subject to a study population analysis group will occur prior to unblinding.
- Where final FSFI-LD data are not available and exceed greater than 5% of the values for comparison, a mixed model regression analysis that includes the dependent variable and one or more auxiliary variables that reflect plausible assumptions around the uncertainty due to missing data will be conducted and subjected to sensitivity analysis.

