### 3.3 Exploratory Endpoints

- Change in FSFI subdomain scores from screening to completion of 4 consecutive weeks of treatment with VR101 or the sham IVR. Point responses (numerical responses) for the set of questions for each domain are summed and then multiplied by the indicated factor for that domain. Individual domain scores at Visit 1 will be subtracted from individual domain scores at Visit 2 to provide a change score. The mean change from baseline for each of the domains will be compared across the study arms using Student's *t*-test.
- Change in total FSFI score from screening to completion of 4 consecutive weeks of treatment with VR101 or sham. Total FSFI reflects overall sexual function and is the sum of all domain scores. The mean change from baseline in total FSFI score will be compared across the study arms using Student's *t*-test.

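### Exploratory FSFI change is compared by a valid t-test that does not adjust for the Visit 1 score, and SAP 6.2 states equal variances above separate-variance (Welch) formulas

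*SAP*

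**What the plan says.** SAP 3.3 forms the exploratory outcome by subtraction: "Individual domain scores at Visit 1 will be subtracted from individual domain scores at Visit 2 to provide a change score". It then states, for the total score, "The mean change from baseline in total FSFI score will be compared across the study arms using" Student's t-test, and plans the same for each domain. SAP 6.2 repeats this and names no covariate.

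Protocol 8.1.2 says of the same analysis that "changes in individual scores will be compared for the two groups using appropriate parametric (independent-test) or nonparametric (Mann-Whitney) statistical methods". Both named methods are unadjusted.

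On variances, SAP 6.2 contains three elements:

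- the words "where equal variances are assumed";
- a standard error of sqrt(s1²/n1 + s2²/n2) and a Satterthwaite-type DF formula written in VAR1 and VAR2, which are not defined;
- Cohen's d, which "is the standardized mean difference using the pooled standard deviation".

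On baseline availability, Protocol 5.4.6 says that at both study visits "each participant will be given the FSFI Survey". Completeness at entry is promised only for the lubrication domain. Protocol 8.7.3 requires that "screening (Day 0) FSFI-LD scores are complete", and inclusion criterion 6 in Protocol 5.3.1 reads "Respond to all 4 individual FSFI Lubrication Questions (7 - 10) with a score of 1, 2, or 3".

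**The concern.** There are two separate issues.

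**Precision.** A change score fixes the coefficient on baseline at 1. ANCOVA estimates that coefficient from the data, and in large samples it is never less precise. The Visit 1 FSFI is already scheduled for every participant, so the exploratory intervals may be wider than they need to be at no saving in data collection.

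**Specification.** The words in SAP 6.2 describe a pooled test, which would use a pooled SD and n1 + n2 − 2 degrees of freedom. The formulas describe Welch's test. The analyst must pick one, and either choice departs from part of the section. SAP 1 requires deviations from the plan to be described in the final report.

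At stake are the width and labelling of exploratory intervals, and nothing in the primary responder comparison.

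**Working it through.** **Inputs.** N = 175 entered treatment (SAP Table 1). Arm sizes are not visible; 88/87 is assumed from 1:1 allocation. The stated minimum is 80 per group (Protocol 1.1 and 8.3, SAP 4.1). The correlation r between Visit 1 and Visit 2, the ratio k = SD(Visit 1)/SD(Visit 2), and the SD ratio between arms are not given in the visible text and are assumed. The plan has no figure of its own to reproduce here.

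**1. Precision.** In units of the Visit 2 variance, a change score has variance 1 + k² − 2rk and the ANCOVA residual has variance 1 − r². The difference is (1 + k² − 2rk) − (1 − r²) = (k − r)², which is never negative and is zero only when r = k. The ratio (1 − r²)/(1 + k² − 2rk) is:

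| k | r=0.2 | 0.3 | 0.4 | 0.5 | 0.6 | 0.7 |
|---|---|---|---|---|---|---|
| 1 | 0.600 | 0.650 | 0.700 | 0.750 | 0.800 | 0.850 |
| 0.75 | 0.760 | 0.818 | 0.873 | 0.923 | 0.966 | 0.995 |
| 0.5 | 0.914 | 0.958 | 0.988 | 1.000 | 0.985 | 0.927 |

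The savings are therefore 15% to 40% at k = 1, under 1% to 24% at k = 0.75, and 0% to 9% at k = 0.5.

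Estimating one covariate multiplies the ANCOVA variance by (N − 3)/(N − 4) = 172/171 = 1.0058, a cost of about 0.6%. When r is close to k, this cancels the gain.

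For Lubrication, entry limits the baseline score to between 4 × 1 × 0.3 = 1.2 and 4 × 3 × 0.3 = 3.6, while Visit 2 can reach 6. A k below 1 is likely there, and the gain is probably small.

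**2. Validity.** In simulation at 88/87 with r = 0.5, the type I error of the unadjusted test was 5.0% (Welch and pooled alike), and 4.7% when one arm's residual SD was doubled. There is no bias to correct.

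**3. Who is analysed.** A woman without a Visit 1 score has no change score, so ANCOVA drops no one whom the t-test keeps. ANCOVA on change and ANCOVA on the Visit 2 score give the same treatment estimate and standard error. In a simulated data set both gave 0.3121 (SE 0.1414).

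**4. Welch against pooled.** The table gives the ratio of 95% CI widths, Welch/pooled, at an SD ratio of 1.5 between arms.

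| Split | Larger SD in smaller arm | Larger SD in larger arm |
|---|---|---|
| 88/87 | 1.003 | 0.999 |
| 95/80 | 1.036 | 0.968 |
| 96/79 | 1.041 | 0.963 |

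With equal SDs the ratio is 1.000 at both 88/87 and 95/80. The 96/79 limit follows from 176 randomized with at least 80 per group, so at most 96/80, less the one woman who could not place the ring.

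The undefined VAR matters little. At 88/87 and SD ratio 1.5, DF is 151.8 if VAR = s²/n and 151.3 if VAR = s².

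**The case against.** The strongest case against the covariate point is that it is a preference. The t-test is valid, prespecified, exploratory, and one of the two methods that Protocol 8.1.2 names. No section promises an adjusted analysis, and the assumed r and k allow a gain anywhere from nothing to 40%. All of that is true. It means the plan contains no error on this score, and that ANCOVA should be recorded as an SAP refinement alongside the named test. It does not remove the case for using a baseline that the trial already collects, because the downside is about 0.6% of variance.

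A second objection is that ordinary ANCOVA itself pools the residual variance across arms, which is the assumption criticised in SAP 6.2. This stands. With an SD ratio of 1.5 and the larger SD in the smaller arm, simulated type I error was 5.0% at 88/87 and 5.6% at 95/80. With an HC3 robust standard error it was 4.6% to 4.8%. The fix therefore specifies a robust standard error.

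Third, the printed SE, DF and interval formulas agree with one another, so the equal-variance phrase may be only a stray remark. That is plausible, but SAP 6.2 also calls the test Student's, so the text does not settle which software option will be run.

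Fourth, a site term would have no demonstrated precision gain, and the primary test is not site-adjusted. This also stands, so site is left optional.

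**Conclusion.** Both parts hold, at minor severity. SAP 3.3 and 6.2 leave precision unused on the exploratory FSFI scores, by an amount that depends on assumed r and k and is probably small for Lubrication. SAP 6.2 also describes one test in words and another in formulas. The consequence is at most 0.3% of interval width near 1:1 and about 3% to 4% at the most uneven split compatible with 80 per group, if the SD ratio between arms is no more than 1.5.

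Three stronger readings are tempting, and the documents do not support them:

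- A reader might infer that the change-score test is biased. Under randomization it is not.
- A reader might infer a larger label effect from a split such as 100/75, where the widths would differ by 5% to 6%. With 176 randomized and one excluded, that implies at most 76 randomized in one arm, below the stated minimum of 80.
- A reader might infer that no adjusted analysis was ever specified. SAP 1 says that Section 10 holds additions to the plan, and part of that section was removed before review, so this cannot be settled. The mixed model in SAP 8.3 does not fill the gap, because it is triggered only by more than 5% missing final FSFI-LD scores.

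The primary responder analysis and the pass/fail criterion are unaffected.

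**What to change.** In SAP 3.3 and 6.2:

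1. Analyse change in each total and domain score (or equivalently the Visit 2 score) by ANCOVA on treatment and the corresponding Visit 1 score, with a heteroscedasticity-robust standard error such as HC3. Report the adjusted mean difference with 95% CI, labelled exploratory. A site term is optional.
2. Keep the t-test named in Protocol 8.1.2 as a supporting analysis and call it Welch's. Delete "where equal variances are assumed", define VAR_i = s_i²/n_i, and state that the pooled SD is used for Cohen's d only.
3. Record ANCOVA as an addition to Protocol 8.1.2. The sponsor should decide whether Protocol 10, which covers changes to data analysis, requires approval for it.

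The cost is SAP wording, one regression per score, and about 0.6% of variance for the extra coefficient at N = 175. No new data are needed. The change belongs before unblinding. If unblinding has already taken place, the report should state which t-test was run and mark ANCOVA as added.

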## 7 ANALYSIS GROUPS

The target population for this study is the subset of women with deficient vaginal moisture/lubrication identified through inclusion and exclusion criteria and ability to independently place and remove an IVR. This is a subset of the broader population who would adhere to treatment with either the VR101 or sham IVR.

### 7.1 Full Analysis Set (ITT) and Modified ITT

The planned full analysis set includes all randomized participants. Because the ability to place and remove the study devices independently is not assessed until after randomization the primary efficacy analysis requires a modified ITT as it will not include participants who are unable to insert a vaginal ring. Subjects with other serious protocol violations will be assessed during the blind review for inclusion or exclusion in the final Modified ITT.

### 7.2 Complete Case Set

The subset of participants in the Modified ITT set who complete all study visits and for whom all outcome measures are collected.

J3 Bioscience, Inc.	Statistical Analysis Plan	CI03-SAP Rev. 00 Page 15 of 31
	CI03: A Clinical Investigation to Evaluate Efficacy of the J3 Bioscience Lubricating Intravaginal Ring VR101 as a Personal Lubricant Device in Women	

### 7.3 Per Protocol Set

The subset of participants in the Modified ITT set who complied with the protocol sufficiently to ensure that data would be likely to represent the effects of the study treatments according to the underlying study model. Participants in this subset meet all inclusion and exclusion criteria, are able to place and remove an IVR independently, use the device as specified, complete both study visits and scheduled interim phone calls with no major protocol violations during 4 weeks of consecutive study device use. Anticipated major protocol violations include use of excluded concomitant medications, vaginal lubrication products, performance of oral sex prior to or during intercourse, and failure to attempt intercourse. Other protocol deviations will be assessed during the blind review of all collected data at the end of the study prior to unblinding. All protocol deviations will be classified as major or minor and will be tabulated for the clinical study report.

## 8 DISPOSITION OF MISSING DATA

### 8.1 Prevention of Missing Data

- Prevention of missing data is central to this study design. All participants will be counseled at enrollment on the importance of completing the study and communicating all issues and concerns to the study coordinator.
- Study staff will provide a “safe” place for disclosure of intent to withdraw from the study so that an Early Termination (ET) visit and final outcome measures can be collected prior to withdrawal of consent.
- If subject safety is assured, non-compliance with study requirements will not require early discontinuation.
- Case report forms will be designed to capture all relevant background information as well as objective reasons for early discontinuation when it cannot be prevented.

### 8.2 Incentive to Complete

- Under the FDA guidance for payment and reimbursement to research subjects, (January 2018) the sponsor will provide a study completion payment similar to the payment for one regular study visit for participants who complete the study per protocol with no missing data (also see final Informed Consent Form dated 31 January 2020).

J3 Bioscience, Inc.	Statistical Analysis Plan	CI03-SAP Rev. 00 Page 16 of 31
	CI03: A Clinical Investigation to Evaluate Efficacy of the J3 Bioscience Lubricating Intravaginal Ring VR101 as a Personal Lubricant Device in Women	

- Participants who complete the 4-week double-blind study will be given the opportunity to continue in a 2-week open label extension where they will be guaranteed to receive the active VR101 device.

### 8.3 Unavoidable Loss of Data

It is expected that any study subject who begins one of the treatment arms following randomization will be included in the primary efficacy analysis. As noted, enrollment in the study and randomization requires that all participants meet inclusion/exclusion criteria, including the Visit 1 FSFI-LD baseline. Initiation of treatment requires ability to independently place an IVR. The primary efficacy outcome, proportion of subjects who have a “functional” score of 4.5 or better after 4 weeks of treatment, is therefore dependent on a post randomization FSFI-LD score.

It is understood that data may still be missing, for anticipated and unanticipated reasons (intercurrent events) that arise during the study. As no universally applicable methods for handling missing values are recommended in guidance documents, methods for handling missing data in this study will be determined by the reasons for “missingness” and predefined by updating the SAP after blind review. Appropriate sensitivity analyses will be specified to evaluate assumptions associated with handling of all missing data.

Where unavoidable, participants who successfully start but cannot complete 4 weeks of treatment will be scheduled for an Early Termination visit so the final (Visit 2) FSFI-LD scores can be collected prior to withdrawal of consent.

For subjects who must drop out prior to providing study endpoint efficacy data, the reason for discontinuation will be ascertained and recorded in the CRF. Prior to data lock and unblinding the status and quality of each subject’s study data will be assessed by the sponsor’s data quality team. The disposition and assignment of each subject to a study population analysis group will occur prior to unblinding.

If final FSFI-LD are not available in excess of 5% of the unblinded data, mixed model regression that includes one or more auxiliary variables reflecting plausible assumptions around the uncertainty due to missing data will be conducted and subjected to sensitivity analysis.

### 8.4 Missing Data by Groups

The reasons why data are missing and whether there are systematic differences in the patterns of missing data across the treatment arms will also be summarized. Group differences will be examined following unblinding and presented in a table for

J3 Bioscience, Inc.	Statistical Analysis Plan	CI03-SAP Rev. 00 Page 17 of 31
	CI03: A Clinical Investigation to Evaluate Efficacy of the J3 Bioscience Lubricating Intravaginal Ring VR101 as a Personal Lubricant Device in Women	

the final study report. This information will also be used to determine whether additional sensitivity analyses are required during data analysis, and if so, the justification for these analyses and the outcomes will be included in the final report.

## 9 PLANNED SENSITIVITY ANALYSES

- An important assumption in this study is that the efficacy outcome, V2 FSFI-LD will distinguish the treatment arms at a “functional” score of 4.5 or better. The primary efficacy analysis is a comparison between proportions of subjects in each arm who reach this level of functionality. To test this assumption around the point estimate of functionality, a similar comparison between groups will be made for the proportion who report scores of 4.2 or better and the proportion who report scores of 4.8 or better.
- Robustness of the findings for point estimate proportions analysis will be assessed by conducting an area under the curve (AUC), Kaplan-Meier survival analysis using frequency data for percentages in each group achieving successively higher scores (4.2 through 6.0) on the Visit 2 FSFI-LD.
- The assumption that ability to place an IVR independently is not impacted by the assigned treatment arm (in other words, VR101 and the sham IVR are equally likely to result in instances of inability to place an IVR) will be tested by comparing the numbers of randomized subjects in each group who were not able to place the IVR, and repeating the primary efficacy analysis but including those subjects in the group denominators for the proportion comparison between groups.

